10.1.8 QUALITY ASSURANCE AND QUALITY CONTROL

Each clinical site will perform internal quality management of study conduct and collection, documentation and completion. All sites will follow a common quality management plan.

Quality control (QC) procedures will be implemented as follows:

Informed consent: Study staff will review both the documentation of the consenting process as well as 100% of the completed consent documents. This review will evaluate compliance with GCP, accuracy, and completeness. Feedback will be provided to the study team to ensure proper consenting procedures are followed.

Source and the electronic documents data: Data will be directly entered into the study database (see Section 10.1.9, Data Handling and Record Keeping).

Intervention Fidelity: Consistent delivery of the study interventions will be monitored throughout the intervention phase of the study. Procedures for ensuring fidelity of intervention delivery are described in Section 6.2.1, Interventionist Training and Tracking.

Protocol Deviations: The study team will review protocol deviations on an ongoing basis and will implement corrective actions when the quantity or nature of deviations are deemed to be at a level of concern.

10.1.9 DATA HANDLING AND RECORD KEEPING

10.1.9.1 DATA COLLECTION AND MANAGEMENT RESPONSIBILITIES

Data collection will be the responsibility of the clinical trial staff at the site under the supervision of the site investigator. The investigator will be responsible for ensuring the accuracy, completeness, legibility, and timeliness of the data reported.

All source documents will be completed in a neat, legible manner to ensure accurate interpretation of data.

Hardcopies of the study visit worksheets will be provided for use as source document worksheets for recording data for each participant consented/enrolled in the study if needed. Data recorded

Adapted from NIH Behavioral and Social Intervention Clinical Trial Protocol Template v3.0 - 20180827

in the electronic case report form (eCRF) derived from source documents will be consistent with the data recorded on the source documents.

Survey data will be entered during client encounters into a REDCap database a 21 CFR Part 11-compliant data capture system provided by the UW. The data system includes password protection and internal quality checks, such as automatic range checks, to identify data that appear inconsistent, incomplete, or inaccurate.

10.1.9.2 STUDY RECORDS RETENTION

Records retention will follow required IRB/ERC and sponsor guidelines.

10.1.10 PROTOCOL DEVIATIONS

This protocol defines a protocol deviation as any noncompliance with the clinical trial protocol, International Council on Harmonization, Good Clinical Practice (ICH GCP), or Manual of Procedures (MOP) requirements. The noncompliance may be either on the part of the participant, the investigator, or the study site staff. As a result of deviations, corrective actions will be developed by the site and implemented promptly.

These practices are consistent with ICH GCP:

- Section 4.5 Compliance with Protocol, subsections 4.5.1, 4.5.2, and 4.5.3
- Section 5.1 Quality Assurance and Quality Control, subsection 5.1.1
- Section 5.20 Noncompliance, subsections 5.20.1, and 5.20.2.

It will be the responsibility of the site investigator to use continuous vigilance to identify and report deviations within 3 working days of identification of the protocol deviation. Protocol deviations will be sent to the reviewing IRB/ERC per their policies. The site investigator will be responsible for knowing and adhering to the reviewing IRB requirements. Further details about the handling of protocol deviations will be included in the MOP.

10.1.11 PUBLICATION AND DATA SHARING POLICY

This study will be conducted in accordance with the following publication and data sharing policies and regulations:

National Institutes of Health (NIH) Public Access Policy, which ensures that the public has access to the published results of NIH funded research. It requires scientists to submit final peer-reviewed journal manuscripts that arise from NIH funds to the digital archive PubMed Central upon acceptance for publication.

This study will comply with the NIH Data Sharing Policy and Policy on the Dissemination of NIH-Funded Clinical Trial Information and the Clinical Trials Registration and Results Information

Adapted from NIH Behavioral and Social Intervention Clinical Trial Protocol Template v3.0 - 20180827

Submission rule. As such, this trial will be registered at ClinicalTrials.gov, and results information from this trial will be submitted to ClinicalTrials.gov. In addition, every attempt will be made to publish results in peer-reviewed journals. In accordance with the NIH Data Sharing Policy, de-identified data will be stored in the National Institute of Child Health and Human Development (NICHD) Data and Specimen Hub (DASH) (<https://dash.nichd.nih.gov>) indefinitely. Data from this study may be requested from other researchers through DASH. Considerations for ensuring confidentiality of these shared data are described in Section 10.1.3.

10.1.12 CONFLICT OF INTEREST POLICY

The independence of this study from any actual or perceived influence, such as by the pharmaceutical industry, is critical. Therefore, any actual conflict of interest of persons who have a role in the design, conduct, analysis, publication, or any aspect of this trial will be disclosed and managed. Furthermore, persons who have a perceived conflict of interest will be required to have such conflicts managed in a way that is appropriate to their participation in the design and conduct of this trial. The study leadership in conjunction with the NICHD has established policies and procedures for all study group members to disclose all conflicts of interest and will establish a mechanism for the management of all reported dualities of interest.

10.2 ADDITIONAL CONSIDERATIONS

NA

10.3 ABBREVIATIONS AND SPECIAL TERMS

AIDS	Acquired Immune Deficiency Syndrome
ALHIV	Adolescents Living With HIV
AMHR	Applied Mental Health Research
ART	Antiretroviral Therapy
CAB	Community Advisory Board
CEO	Chief Executive Officer
CFAR	Center For AIDS Research
CFIR	Consolidated Framework for Implementation Research
CRT	Cluster Randomized Trial
CCC	Comprehensive care clinic

Adapted from NIH Behavioral and Social Intervention Clinical Trial Protocol Template v3.0 - 20180827

DiSC	Data Informed Stepped Care
DSMB	Data Safety and Monitoring Board
EMR	Electronic Medical Records
ERC	Ethical Review Committee
FGD	Focus Group Discussion
GEE	Generalized Estimating Equations
HCW	Health Care Worker
HIV	Human Immunodeficiency Virus
HS	Health Systems
HSD	Human Subjects Division
IDI	In-Depth Interview
IRB	Institutional Review Board
IRDO	Impact Research and Development Organization
IS	Implementation Science
KNH	Kenyatta National Hospital
LTFU	Loss To Follow Up
MoH	Ministry of Health
NICHD	National Institutes of Child Health and Development
NIH	National Institutes of Health
NASCOP	National AIDS and STI Control Program
RE-AIM	Reach, Effectiveness, Adoption, Implementation and Maintenance
RCT	Randomized Controlled Trial
sSA	Sub-Saharan Africa
UNAIDS	Joint United Nations Programme on HIV/AIDS
US	United States
UW	University of Washington

Adapted from NIH Behavioral and Social Intervention Clinical Trial Protocol Template v3.0 - 20180827

VL

Viral load

WHO

World Health Organization

10.4 PROTOCOL AMENDMENT HISTORY

The table below is intended to capture changes of IRB-approved versions of the protocol, including a description of the change and rationale. A Summary of Changes table for the current amendment is located in the Protocol Title Page.

Version	Date	Description of Change	Brief Rationale
2.0	20-Dec-2020	Updated the protocol to address questions from MU ERC. These include updates to consent forms 05, 06, & 07; updated ages for providing consent;	To address comments from MU ERC.
3.0	13-May-2021	Asked for waiver of written consent for participation in intervention	MUERC did not approve for waiver of written consent
3.0	3-Aug-2021	Submitted additional consents for participation in intervention	MUERC approved additional consents for participation in intervention

1.1. Rationale

UNAIDS '95-95-95' targets cannot be achieved without additional support for adolescents living with HIV (ALHIV) to increase retention in care and to support viral suppression. A stepped care approach to care can support allocation of ALHIV to tailored care based on risk.

This study aims to test a data-informed stepped care approach to improve retention among ALHIV. We will also study HIV cascade outcomes (viral non-suppression, receiving differentiated care, adherence).

1.2. DiSC Cluster RCT Objectives

Primary: To compare retention during 12-month follow-up among ALHIV in 12 HIV clinics receiving DiSC intervention to retention among ALHIV in 12 similar control clinics receiving standard of care. Participating clinics will be high-volume HIV clinics in Homabay, Kisumu and Migori counties, all in Western Kenya.

Secondary: To evaluate the effect of the DiSC intervention on HIV cascade outcomes (viral non-suppression, receiving differentiated care, adherence).

Section 2. Study outcomes

2.1. Summary of primary and secondary outcomes

Table 1. Outcome definitions and assessment

Outcome	Indicator	Source	Timing
Primary outcome			
Retention in care	Missed visits: Not seen within 30 days of a scheduled visit.	EMR data (Visit Date, TCA)	All visits occurring during the 12-month period after the study enrollment visit*
Secondary outcomes			
Loss to follow-up	Not return to care within the 12 months study interval	EMR data (Visit Date, TCA)	All visits after the first study visit until event or end of follow-up at 12 months. Participants marked as 'transferred out' or 'died' will be censored.
Viral non-suppression	Having HIV viral load (VL) >1,000 copies/mL	NASCOP data, abstraction of paper records	All visits from enrollment to 12 months follow-up*
Receiving differentiated care	
 Long inter-visit interval Fast-track visit 	EMR data (TCA, Care Model)	All visits from enrollment to 12 months follow-up*
Adherence	Pill coverage estimated by days of dosing and inter-visit interval since last visit >80%	EMR data (Visit Date, next Visit Date, Duration)	All visits from enrollment to 12 months follow-up*

*time window up to 12 months + 30 days

2.2. Sample size considerations

2.2.1. Sample size and power for primary outcome

In our sample of HIV care facilities with >1,000 clients enrolled overall, we anticipate at least 10% will be eligible adolescents and young adults (AYA), with about 100-200 AYA per clinic on average. Based on our UG3 data, we assume that 75% will be in care (not LTFU) by the end of 12-month follow-up period. Given a minimum of 24 facilities in the trial (minimum 12 per arm), we estimated the minimum average number of AYA per facility to detect a 14-18% point change in retention using EMR data. Assuming 12 facilities per arm, 80% power, $\alpha=0.05$ and coefficient of variation of 0.10 (Table 2), we can detect a 14%-point difference (75% to 89%) with at least 150 AYA per facility, and a 15%-point difference (75% to 90%) with at least 50 AYA per facility. Assuming coefficient of variation of 0.15, we can detect a 17%-point difference (75% to 92%) with at least 50 AYA per facility (Table 2). Detecting a less than 14%-point difference or if assuming a larger correlation coefficient of individuals within a facility would require more participants per facility or more facilities per arm.

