4.3 JUSTIFICATION FOR INTERVENTION

The intervention will be delivered by HCW during routine clinical visits; and works at improving clinic level effectiveness in care management. We anticipate at least 50 adolescents per site will be exposed to the intervention during the course of the study period. The intervention will be offered during regular clinic visits that are typically scheduled 1-6 monthly.

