3.4. Analysis of retention

Retention will be evaluated using an indicator of missed visits. A missed visit will be defined as a participant not seen within 30 days of a scheduled visit during follow-up since the first stepped care visit to 12 months. Each scheduled visit will be classified as missed versus not missed and analysis will use repeated measures per participant. The proportion of missed visits will be compared between study arms using mixed-effects Poisson regression with random effects for facility and participant and robust standard errors.

Sub-group analyses for retention will be performed by gender and age-group. Facility factors, including concurrent adolescent-friendly services and high/low performance will be evaluated as modifiers of intervention effectiveness.

Table 4. Analysis of missed visits

	Overall	Control	Intervention	Intervention vs. control
Missed visits per participant				^a RR (95% CI)
Median (IQR)				
Number of scheduled visits				
Number of missed visits (%)				
Missed visits over all participants				
Count (proportion)				
Number of scheduled visits				
Number of missed visits (%)				
Number of AYA ever missed a visit (%)				

^a Estimated by mixed-effects Poisson regression with random effects for facility and participant and robust standard errors

*Excluding TCA that had miss/no-miss status censored or missing

*Models adjusted for any factors differing between arm with statistical significance at enrollment

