3.5. Analysis of secondary study outcomes

3.5.1. Loss to follow-up:

- Loss to follow-up will be defined as a participant missed a visit and did not return to care within the 12-month study period. The proportion of loss to follow-up during 12-month study interval (window up to 12 months +30 days) will be compared between study arms using Poisson regression with robust errors.
- Time to loss to follow-up will be compared between arms by survival curves, and death or transfers will be censored. The hazard of loss to follow-up will be compared between study arms using Cox proportional hazards regression.

3.5.2. Viral non-suppression:

- Viral non-suppression will be defined as having HIV viral loads (VL) >1,000 copies/mL. Each VL testing result will be classified as VL suppressed vs. unsuppressed. The proportion of viral non-suppression during follow-up will be compared between study arms using mixed-effects Poisson regression with random effects for facility and participant and robust standard errors.

3.5.3. Receiving differentiated care:

- Receiving differentiated care will be defined in two ways. One approach will evaluate the next visit appointment date (scheduled inter-visit interval) – visits scheduled for ≥ 3 months after visit will be considered as differentiated care, in comparison to monthly visits recommended for AYA in current guidelines. The second approach will use the variable ‘fast-track’ at each visit – ‘fast track’ visits are considered as a component of differentiated care. Two analyses will be conducted (one for long scheduled inter-visit interval and one for ‘fast track’), each will be compared between study arms using mixed-effects Poisson regression with random effects for facility and participant and robust standard errors.

3.5.4. Adherence:

- Adherence will be evaluated using the proportion of days of pill dosing over days of inter-visit interval. The level of adherence during the past inter-visit interval will be assessed at each visit. A proportion over 80% as good adherence. The dichotomized adherence will be compared between arms using mixed-effects Poisson regression with random effects for facility and participant and robust standard errors.

Table 5. Analysis of secondary study outcomes

Loss to follow-up				
	Overall	Control	Intervention	Intervention vs. control
	Count (proportion)			^a RR (95% CI) ^b HR (95% CI)
Event Person-year Cumulative incidence Incidence rate (per 100 person-years)				
Viral non-suppression				

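### SAP 2.2.1 is headed power for the primary outcome but sizes 12-month loss to follow-up, a secondary outcome; no detectable effect is stated for missed visits, the primary outcome

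*SAP*

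**What the plan says.** - **Primary outcome (SAP 2.1, outcome table).** Retention in care, with the indicator "Missed visits: Not seen within 30 days of a scheduled visit". LTFU is listed separately as secondary.
- **Primary analysis (SAP 3.4).** "The proportion of missed visits will be compared between study arms using mixed-effects Poisson regression with random effects for facility and participant", with robust standard errors. Every scheduled visit is classified, and the result is an RR with 95% CI.
- **LTFU (SAP 3.5.1).** "Loss to follow-up will be defined as a participant missed a visit and did not return to care within the 12-month study period".
- **Power.** Under the heading "2.2.1. Sample size and power for primary outcome", the control value is introduced as "we assume that 75% will be in care (not LTFU) by the end of 12-month follow-up period". Detectable values for 12 facilities per arm follow: with "coefficient of variation of 0.10 (Table 2), we can detect a 14%-point difference (75% to 89%) with at least 150 AYA per facility", then 75% to 90% with 50 per facility, and 75% to 92% with 50 per facility at 0.15.
- **Clustering label.** The text of 2.2.1 and 2.2.2 and the table footnote call 0.10 and 0.15 a coefficient of variation. The table column is headed ICC, and 2.2.1 closes by speaking of a within-facility correlation.
- **Viral load.** SAP 2.2.2 sizes a change from 64% to 82% suppressed. Protocol 9.2 derives 64% as 85% suppressed times 75% in care. SAP 3.5.2 classifies each result obtained, and SAP Section 4 rules out formal imputation.

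**The concern.** LTFU and missed visits are different quantities. A participant who is late by more than 30 days and then returns adds a missed visit but is not lost. One outcome has a single value per person. The other has several, with correlation within person and within clinic. A base rate and an ICC for LTFU therefore say nothing definite about missed visits.

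A reader of 2.2.1 will take 14 to 18 points as what the trial was sized to find on its primary outcome. Whether a change of that size in missed visits is large, small or even possible depends on a control rate that neither document gives. The visits per participant used for sizing and the visit-level correlations are also absent.

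The two lesser faults could mislead in the same section. The SAP and Protocol use one term for two different clustering measures, and the viral-load statement describes a contrast that the analysis will not make.

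**Working it through.** **1. Reproduce the SAP's figures.** Inputs from SAP 2.2.1 and 2.2.2: 80% power and alpha 0.05 (two-sided assumed), so the squared sum of normal quantiles is 7.849; m participants per facility.

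Facilities per arm = 7.849 × (p0q0 + p1q1)/d² × [1 + (m − 1) × ICC]/m

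- 75% to 89%, m = 150, ICC 0.10: 7.849 × 0.2854/0.0196 × 15.9/150 = 12.11 (table: 12; power with 12 is 79.6%)
- 75% to 90%, m = 50, ICC 0.10: 7.849 × 0.2775/0.0225 × 5.9/50 = 11.42 (table: 12; power 81.9%)
- 75% to 92%, m = 50, ICC 0.15: 7.849 × 0.2611/0.0289 × 8.35/50 = 11.84 (table: 12; power 80.5%)
- 64% to 82%, m = 50, ICC 0.10: 7.849 × 0.378/0.0324 × 5.9/50 = 10.81 (table: 11)

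Rounded up, this formula matches 141 of the 144 table cells. The other three are rounding (12.11 printed 12, 9.003 printed 9, 13.05 printed 13).

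**2. Test the label.** With k a between-clinic coefficient of variation:

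Facilities per arm = 1 + 7.849 × [(p0q0 + p1q1)/m + k²(p0² + p1²)]/d²

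The four contrasts above give 7.19, 7.72, 11.03 and 5.45, and only 5 of 144 cells match. The same formula with k = 0.15 gives 12.74, 10.32 and 9.39 at m = 100, and 13.71, 11.03 and 10.004 at m = 50. These are Protocol Table 3a's 13, 11, 10 and 14, 12, 10. So the Protocol used a true CV, and the SAP uses ICCs under the old name. At 75% the conversion is ICC = k² × p/(1 − p), so a CV of 0.15 is an ICC of 0.0225 × 3 = 0.0675, not 0.15.

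**3. Set the powered quantity beside the primary outcome.**

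- Powered: share of participants not LTFU at 12 months, control 75%, one value each.
- Primary: share of scheduled visits missed, control rate not given, repeated values per participant, effect as RR.

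Nothing in either document converts the first into the second.

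**4. Illustrate what is missing.** All inputs here are assumptions except 12 clinics per arm and a clinic size inside the SAP's range ("with about 100-200 AYA per clinic on average"): 150 per clinic, v = 4 visits each, within-participant correlation 0.2. A cluster-level t test on 22 df stands in for the planned Poisson model.

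Variance of a clinic's proportion = pq × [1 + (v − 1) × 0.2 + (m − 1) × v × ICC]/(m × v)

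At ICC 0.05 the bracket is 1 + 0.6 + 149 × 4 × 0.05 = 31.4. From 25% missed to 14.2%, the standard error is √[(0.1875 + 0.1220) × 31.4/7,200] = 0.0367. The difference of 0.108 is 2.93 standard errors, which gives 80% power.

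- From 25% missed, clinic ICC 0.02 / 0.05 / 0.10: detectable fall 7.3 / 10.8 / 14.4 points, RR 0.71 / 0.57 / 0.43.

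Varying 100 to 200 per clinic, 2 to 12 visits (Protocol 4.3: "regular clinic visits that are typically scheduled 1-6 monthly") and within-participant correlation 0.1 to 0.4 moves these falls by at most about 0.6 points. Base rate and clinic ICC decide the answer, and both are missing.

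**5. Viral load.** 0.85 × 0.75 = 0.6375, the Protocol's 64%. If 85% were the suppressed share among those tested, the largest possible gain is 15 points, so an 18-point gain cannot occur. On the SAP's own normal basis (12 per arm, ICC 0.10, one result for each of 50 people per clinic), the detectable level from 85% is about 96.3%.

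**The case against.** **The power basis is not unrelated to the primary objective.** The Protocol synopsis gives the primary endpoint as the percentage retained at 6 and 12 months, and Protocol 9.4.2 puts both missed visits and a Cox analysis of LTFU under the primary endpoint. The SAP also uses the word retention for both. This stands as an explanation: the basis appears to have been carried over and not updated. It does not rescue SAP 2.2.1, because the SAP itself makes missed visits primary and LTFU secondary.

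**A reader might infer that the trial is underpowered for its primary outcome.** The documents do not support that. The illustration at 25% missed and ICC 0.10 gives 14.4 points, close to the SAP's 14, and lower ICCs give smaller detectable falls.

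**A reader might infer that if missed visits are rare, even their elimination would go undetected.** The formula in step 4 can suggest this at 5% missed and ICC 0.10, but it fails there. The between-clinic SD, √(0.10 × 0.05 × 0.95) = 6.9 points, exceeds the mean. A simulation with beta-distributed clinic rates gave about 89% power for a fall to zero. At 10% missed and ICC 0.10, the formula's detectable RR of 0.13 had about 88% simulated power rather than 80%, so that value is unreliable too.

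**A reader might infer that a null result could not be interpreted.** It could: the planned RR and 95% CI show which effects are excluded.

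**A reader might infer that the LTFU power claims fail.** On the SAP's normal basis they hold (79.6% to 81.9%). With t on 22 df they fall to 76.0%, 78.4% and 76.9%, but that is a choice of approximation and at most an optional sensitivity check.

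**The label is a wording matter.** Agreed: the table's arithmetic is right for an ICC, and the label does not overstate power. The footnote's 0.10 might have been meant as variation in cluster size, but the documents do not say so, and that reading cannot explain the 0.15 in the text.

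**The viral-load link is partly inferred.** The SAP does not derive its 64%; the identical Protocol figure is the basis. The threshold behind the 85% is not stated.

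**Conclusion.** The point holds as a mismatch between the power statement and the SAP's primary outcome. The 14 to 18 point differences apply to 12-month LTFU. The detectable effect on missed visits is not stated and cannot be derived from the documents, so its direction relative to the LTFU figures is unknown. The RRs of 0.71, 0.57 and 0.43 are illustrations that rest on an assumed 25% base rate, assumed correlations and a cluster-level approximation.

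The clustering label is wrong in the SAP text and footnote, without numerical consequence for the SAP table. The viral-load statement describes a composite, on the inference that its 64% is the Protocol's, and not the share among results obtained. This should be corrected before analysis; it does not call the design into question.

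**What to change.** 1. Label the existing retention figures in SAP 2.2.1 as applying to 12-month LTFU.
2. Add a detectable RR or difference for missed visits over a short range of base rate, scheduled visits per participant, clinic ICC and within-participant correlation. The baseline EMR abstraction (Protocol 8.1), pooled over arms, is one possible source. Use simulation or the planned model where the base rate is low and the ICC high.
3. Replace coefficient of variation with ICC in SAP 2.2.1, 2.2.2 and the table footnote.
4. Restate viral-load detectability from the suppressed share among tested results at the SAP's threshold of >1,000 copies/mL, with the assumed number of results per person.

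The cost is SAP wording, one added set of calculations for missed visits from data already planned for abstraction, and a recalculated viral-load statement. Endpoints, clinics and participants stay as they are.

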9.2 SAMPLE SIZE DETERMINATION

Sample Size and Power for primary outcome

In our sample of HIV care facilities with >1,000 clients enrolled overall, we anticipate at least 10% will be eligible adolescents and young adults or about 100-200 AYA per clinic on average. Based on our UG3 data, we assume that 75% will be in care (not LTFU) and viral suppression of 64% (85% suppressed x 75% actively in care). Given a minimum of 20 facilities in the trial (minimum 10 per arm), we estimated the minimum average number of AYA per facility to detect a 15-20% change in retention using EMR data. We assumed 80% power, an $\alpha=0.05$ and coefficient of

Adapted from NIH Behavioral and Social Intervention Clinical Trial Protocol Template v3.0 - 20180827

variation of 0.15. In table 3a below, we can detect a 17% percentage point different (75% to 93%) with an average of 100 AYA per facility and 20 facilities. The same estimates hold for as few as 50 AYA per arm and up to 170 per arm. Detecting less than a 17% percentage point difference would require more facilities per arm or at least 180 AYA per facility.

Secondary outcomes and assumptions:

Viral suppression: An average of 50 AYA VL records per facility and a minimum of 10 facilities per arm would be sufficient to detect a change from 64% to 81%, assuming 80% power, an $\alpha=0.05$ and coefficient of variation of 0.15.

Cohort analyses: Based on UG3 enrollment data in the AYA cohort, we assume that about 50% of the total AYA clinic population to enroll in the cohort and set 50 as the average enrollment target per facility. Separate power and sample size calculations will be performed based on the specific exposure and outcome. When the intervention is the exposure, we will assume to have adequate power to detect at least a 17% percentage point difference in proximate outcomes (e.g. implementation and client outcomes)

Table 3a: Minimum Sample of AYA per Facility for the Primary ITT Analysis of Retention

	Retention % in the intervention arm	n=100 AYA per facility	Facilities per arm	n=50 AYA per facility	Facilities per arm
75%	90%	100	13	50	14
75%	92%	100	11	50	12
75%	93%	100	10	50	10

Table 3b: Summary of sample size estimates by outcome

Outcome	Source	Sample size	
		Intervention	Control
Retention	EMR data	3000	3000
Unsuppressed VL	EMR data	3000	3000
Mediators and secondary outcomes	Adolescent surveys	1500	1500
	Caregiver surveys	450	450
Implementation outcomes	HCW surveys	120	120
	HCW implementation logs	12	0

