2.2.2. Secondary outcomes and assumptions

Viral suppression: An average of 50 AYA VL records per facility and a minimum of 12 facilities per arm would be sufficient to detect a change from 64% to 82%, assuming 80% power, an $\alpha=0.05$ and coefficient of variation of 0.10 (Table 2).

Table 1. Sample size calculation of number of facilities per arm for the ITT analysis of retention and viral suppression

AYA per facility	ICC	Estimated proportion in study arm									
		Control	Intervention								
		75%	85%	86%	87%	88%	89%	90%	91%	92%	93%
200	0.10		26	21	18	15	12	11	9	8	7
150			27	22	18	15	12	11	9	8	7
100			27	22	18	15	13	11	9	8	7
50			30	24	20	17	14	12	10	9	8
	0.15	75%	85%	86%	87%	88%	89%	90%	91%	92%	93%
200			39	31	26	21	18	15	13	11	10
150			39	32	26	22	18	16	13	12	10
100			40	32	26	22	19	16	14	12	10
50			42	34	28	23	20	17	14	12	11
		64%	80%	81%	82%	83%	84%	85%	86%	87%	88%
200	0.10		13	11	10	9	8	7	6	6	5
150			13	12	10	9	8	7	7	6	5
100			13	12	10	9	8	7	7	6	5
50			15	13	11	10	9	8	7	7	6
	0.15	64%	80%	81%	82%	83%	84%	85%	86%	87%	88%
200			19	17	15	13	12	10	9	8	8
150			19	17	15	13	12	10	9	8	8
100			19	17	15	13	12	11	10	9	8
50			20	18	16	14	12	11	10	9	8

ICC: intraclass correlation coefficient; sample size estimated by assuming study power of 80%, significance level of 0.05 and coefficient of variation of 0.10

Section 3. Study Data Analysis

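### The SAP labels an intraclass correlation as a coefficient of variation, so its 0.10 power statements are wrong as labelled; protocol 9.2 calls 75% to 93% a 17-point difference when it is 18

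*SAP*

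**What the plan says.** **SAP.** Section 2.2.1 assumes 12 facilities per arm, 80% power and alpha 0.05. Its first statement is for a "coefficient of variation of 0.10 (Table 2), we can detect a 14%-point difference (75% to 89%) with at least 150 AYA per facility". It then gives 75% to 90% with 50 AYA at the same input, and 75% to 92% with 50 AYA when the input is 0.15. The paragraph closes by warning that "assuming a larger correlation coefficient of individuals within a facility would require more participants per facility or more facilities per arm". Section 2.2.2 says that 50 viral load records per facility are "sufficient to detect a change from 64% to 82%, assuming 80% power", again with a coefficient of variation of 0.10. The table that supports all this is cited as Table 2 but captioned Table 1. Its row blocks are headed ICC, with values 0.10 and 0.15, and its footnote reads "ICC: intraclass correlation coefficient; sample size estimated by assuming study power of 80%, significance level of 0.05 and coefficient of variation of 0.10".

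**Protocol.** Section 9.2 uses a coefficient of variation of 0.15 and at least 10 facilities per arm. It says "we can detect a 17% percentage point different (75% to 93%) with an average of 100 AYA per facility and 20 facilities", and then "The same estimates hold for as few as 50 AYA per arm and up to 170 per arm". Table 3a gives facilities per arm at 100 and 50 AYA per facility: 13 and 14 for 75% to 90%, 11 and 12 for 75% to 92%, and 10 and 10 for 75% to 93%.

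**The concern.** A between-facility CV and an ICC are different quantities and give different sample sizes at the same numerical value. At 75% retention a CV of 0.10 is an ICC of 0.03, and an ICC of 0.10 is a CV of 0.18. The SAP text names one and its table names the other, while the protocol uses the SAP's term with different results.

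Clustering is the main design assumption in a trial of 24 clinics. If the label is wrong, anyone who sets the observed clustering against the planned value when the trial is reported, or who reuses the planning figure, will use the wrong benchmark. In the protocol, the stated effect and the stated pair of proportions differ by one point, and that point decides whether 10 facilities per arm reach 80% power.

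**Working it through.** **Inputs.** Alpha 0.05 and 80% power (both documents). Two-sided testing is assumed, since sidedness is not stated. So (1.960 + 0.842)² = 7.849. Control retention is 75%. Facilities per arm are 12 (SAP) and 10 (protocol). Below, m is the number of AYA per facility and c the number of facilities per arm.

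**Formulas.**
- ICC reading: `c = 7.849 × [p0(1−p0) + p1(1−p1)] / (p1−p0)² × [1 + (m−1)·ICC] / m`, rounded up.
- CV reading (Hayes–Bennett): `c = 1 + 7.849 × {[p0(1−p0) + p1(1−p1)]/m + k²(p0² + p1²)} / (p1−p0)²`, rounded up.
- Conversion at proportion p: `ICC = k²·p/(1−p)`. At 75%, k = 0.10 gives 0.01 × 3 = 0.03 and k = 0.15 gives 0.0675. In reverse, ICC 0.10 gives k = √(0.10/3) = 0.18.

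**1. Which parameter produced the SAP table?** The ICC formula matches 141 of 144 cells. The three misses are each one facility out: 75% to 89% at 150 AYA (12.11, printed 12), 75% to 91% at 100 (9.003, printed 9) and 64% to 80% at 100 (13.05, printed 13), all at 0.10. The CV formula matches 5 of 144. Treating the footnote's 0.10 as variation in cluster size, added to the ICC, matches 121.

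**2. The quoted SAP cell, both ways** (75% to 89%, m = 150, input 0.10). The binomial variances sum to 0.1875 + 0.0979 = 0.2854, and (p1−p0)² = 0.0196.
- ICC: 7.849 × 0.2854/0.0196 = 114.3; times (1 + 149 × 0.10)/150 = 0.106; gives 12.11.
- CV: 0.2854/150 = 0.00190; 0.01 × (0.5625 + 0.7921) = 0.01355; sum 0.01545; 1 + 7.849 × 0.01545/0.0196 = 7.19.

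**3. All four SAP statements.** Power is at 12 per arm, by the same normal approximation.

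| Statement | Input | Facilities needed, ICC | Facilities needed, CV | Power, ICC | Power, CV |
|---|---|---|---|---|---|
| 75% to 89%, m = 150 | 0.10 | 12.11 | 7.19 | 79.6% | 96.2% |
| 75% to 90%, m = 50 | 0.10 | 11.42 | 7.72 | 81.9% | 94.8% |
| 64% to 82%, m = 50 | 0.10 | 10.81 | 5.45 | 84.0% | 99.3% |
| 75% to 92%, m = 50 | 0.15 | 11.84 | 11.03 | 80.5% | 83.5% |

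Under a true CV of 0.10, the retention differences detectable with 80% power at 12 per arm would be 10.3 points (150 AYA) and 11.7 points (50 AYA), not 14 and 15. The 0.15 statement needs 12 per arm on either reading.

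**4. Which parameter produced protocol Table 3a?** The CV formula with k = 0.15 gives, at 100 and 50 AYA:
- 75% to 90%: 12.74 and 13.71 (printed 13 and 14)
- 75% to 92%: 10.32 and 11.03 (printed 11 and 12)
- 75% to 93%: 9.39 and 10.00 (printed 10 and 10)

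An ICC of 0.15 would give 15.3 for the first cell; the SAP's 0.15 rows print 16 for it. The protocol's viral suppression statement (64% to 81%, m = 50, k = 0.15) needs 9.60, so 10 per arm is right there.

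**5. The protocol's 17 points.** 93 − 75 = 18. For a true 17-point effect (75% to 92%) at 10 per arm and k = 0.15, power is 75.6% at 50 AYA, 78.6% at 100 and 79.9% at 170. The exact detectable differences are 18.0, 17.3 and 17.03 points, reaching 17.00 at about 180 AYA. Table 3a itself asks for 11 or 12 facilities per arm for 75% to 92%.

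**The case against.** The strongest reply is that the SAP half is labelling. Each text figure is read correctly from the ICC rows, the footnote defines ICC, and 2.2.1 itself mentions correlation within a facility, so a careful reader can recover the meaning. The literal reading gives more power than claimed, so nothing is oversold. No interim analysis or sample size re-estimation depends on the value. All of that is fair, and it limits the consequence. It does not make the statements right as written, and it does not help a reader who meets the same term in the protocol, where it means a true CV.

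On the protocol, the printed pair 75% to 93% does have 80.0%, 82.7% and 83.8% power at 50, 100 and 170 AYA with 10 per arm. The calculation is therefore sound and only the number 17 is wrong. The shortfalls at 100 and 170 AYA are small. Ten per arm is also a minimum: at the planned 12, Table 3a supports 75% to 92% with 50 AYA. These points stand.

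The match counts depend slightly on rounding. Using 7.84 for 7.849 gives 142 matches instead of 141 and takes the protocol's 10.004 just below 10. The 79.6% for the 14-point statement is likewise within approximation error of 80%. Neither affects the conclusion.

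**Conclusion.** Both parts hold. The SAP table was built on ICCs of 0.10 and 0.15, while the text and footnote call the input a coefficient of variation. The three statements at 0.10 are wrong as labelled: they imply 95% to 99% power, not 80%. The statement at 0.15 survives either reading. The footnote's single value of 0.10 does not cover the rows at 0.15. The protocol used a true CV of 0.15 (ICC about 0.07 at 75%), so the two documents use one term for two assumptions, and their requirements for 75% to 90% at 100 AYA differ by three facilities per arm.

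In the protocol, the difference is 18 points. Only the 18-point row fits 10 facilities per arm at both 50 and 100 AYA, and the counts of 50 and 170 should be per facility. Nothing here shows that the trial is underpowered at 12 facilities per arm. The figures assume two-sided testing, equal cluster sizes and the normal approximation; the documents do not name the formula or software used.

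**What to change.** **SAP 2.2.1, 2.2.2 and the table footnote.** Once the sponsor has confirmed what was entered in the calculation, replace coefficient of variation with ICC, and give both 0.10 and 0.15 in the footnote. Add a sentence that the protocol's calculation used a between-facility CV of 0.15. Make the table's caption and citations agree. It is worth noting that at an ICC of 0.10 the 14-point statement has about 79.6% power with 150 AYA and reaches 80% at about 180; this is a refinement, not an error.

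**Protocol 9.2.**
- State that 10 facilities per arm detect 18 points (75% to 93%) for 50 to 170 AYA per facility, on the table's whole-point grid.
- State that 17 points (75% to 92%) needs 11 facilities per arm with 100 AYA, 12 with 50 AYA, or about 180 AYA per facility at 10 per arm.
- Change per arm to per facility for the counts of 50 and 170.
- Bring the following sentence on differences below 17 points into line, and tie the 17-point claim for cohort outcomes to a stated control proportion.
- Leave the viral suppression change of 64% to 81%, which is 17 points and is correctly sized.

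The cost is wording and restated figures. Enrolment, the number of facilities and the analysis do not change.
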